Trail registration number NCT03829228

1. Introduction

Qi is a central concept of traditional Chinese medicine (TCM) and was first documented in the oldest TCM writings more than 2000 years ago. Generally speaking, Qi refers to the vital energy of the body and is derived from two primary sources: 1) inborn Qi (that may be construed as genetics), and 2) pectoral Qi (can be construed as metabolism). Moreover, Qi manifests itself in two forms: Nutritive Qi and Protective Qi (PQi), which can be understood to reflect an individual's nutritional state and immune health, respectively. Regarding the latter, PQi functions to defend the body from the invasion of external pathogens. In the language of TCM, PQi is associated with Yang (as opposed to Yin) and metal (as opposed other elements such as water, wood, fire, and earth). TCM also emphasizes that PQi works primarily on the body surface as a defensive barrier. In this context, PQi is analogous to the anatomical barriers and immune cells of the innate immune system located for example, at the mucosal surfaces of the respiratory and digestive tract. Protective Qi deficiency (PQD) manifests as a predisposition to cold* (*, as defined in TCM), susceptibility to wind* (that carries pathogens), abnormal sweating, and fatigue. Clinical examination of individuals with PQD reveals a feeble or weak pulse as well abnormal tongue features such as the appearance of a thin whitish coating, atypical thickness, and uncharacteristic teeth marks on the side. The individual's face often lacks gloss. Notably, these manifestations are mild, may happen to many people and, from the perspective of western medicine, may not in fact warrant diagnosis of an individual as being sick. If left untreated however, TCM indicates that a worsening of symptoms may ensue, such as the onset of coughing, fever, headache, delirium, bleeding, etc. In this regard, the identification of an individual with PQD is viewed as an aspect of disease prevention in TCM.

TCM has developed a number of methods to strengthen the PQi. Among these is the use of Reishi, either alone or in combination with other TCM remedies. Although there is no definitive data on the treatment duration of Reishi or Reishi-containing formulas needed for improving PQi, anecdotal reports are available that claim significant improvement within days. Notably, Western medicine has identified immune-boosting properties of Reishi, which may explain the PQi enhancing effects of this plant. Specifically, β -glucan – a component of Reishi - has been shown to activate macrophages (1-3), neutrophils (4, 5) and other immunocytes (6-8), and may exhibit particular benefits among macrophage-rich organs such as the lung, liver and spleen. In fact, β -glucans from sources other than Reishi, such as the baker's yeast, are able to initiate similar immune responses and clinical benefits (9).

A notable feature of TCM is that the diagnosis of sickness and disease is made based upon the signs and symptoms observed by doctors and reported by patients. As such, the diagnostic criteria used in the identification of sickness and disease are largely qualitative in nature; there are few established standards that quantitatively evaluate an individual's health status. Hence, there is a need to develop diagnostic

methods that incorporate the principles of TCM, but which also incorporate standardized, quantifiable evaluations. Such evaluations would measure the magnitude of signs and symptoms, thereby providing a more consistent diagnostic tool that would be less subject to the biases and subjectivity of individual clinicians, and could be more uniformly applied across large populations.

The overlap of TCM and western medicine concerning the beneficial effects of Reishi for its Qi enhancing and immune-modulating effects, respectively, has prompted us to investigate whether or not Reishi, in conjunction with other natural products used in TCM, can enhance an individual's PQi. More specifically, if a commercially available dietary supplement (Proglucamune, USANA Health Sciences) containing powdered Reishi and Shitake mushrooms as well as Baker's yeast extract, and which is comprised of 25% β -glucans by weight, will improve an individual's PQi.

The aim of this preliminary study is to provide proof-of-principle of the effect β -glucan on PQD in adults. The secondary objective is to explore the feasibility of studying β -glucan's effect on improving Generic Qi (GQi) via the standardized method and via conventional method

2. Methods and analysis

2.1 Study design

This proof-of-concept and feasibility study is a non-randomized study, and will employ a one-group pretest posttest design. The participants will receive the β -glucan intervention. The study will follow guidelines of the Declaration of Helsinki and Tokyo for human subjects, and reported using Standard Protocol Items: Recommendations for Pilot or Feasibility Trials reporting template (CONSORT 2020) [10]. Throughout the study, all participants will be accessed by a single TCM practitioner, who had been practicing TCM for over 25 years and had received Good Clinical Practice (GCP) training (<https://gcp.nidatraining.org>) prior to the study.

2.2 Participants

The number of recruited participants is determined with reference to previous β -glucan studies that reported a significant effect on UTRI [11-14].

2.2.1 Inclusion criteria

1. Male or females aged 18 to 65 years (inclusive) without regard to race or ethnic background
2. Provide a signed Informed Consent prior to entry in the study.
3. Willing to follow all study instructions and consume the assigned investigational product for 12 weeks.

4. Not currently taking a β -glucan containing supplement or any other supplement that might interfere with the study design.
5. Ability to swallow tablets and pills.
6. Diagnosed as having Qi deficiency based on the following criteria:
 - exhibit a history of susceptibility to cold*
 - exhibit a shortness of breath
 - exhibit a lack of energy or excessive fatigue
 - susceptible to spontaneous perspiration
 - exhibit a corpulent tongue with or without white fur
 - unwillingness to speak
 - weak or powerless pulse
 - pale complexion

2.2.2 Exclusion criteria

1. Persons diagnosed by TCM as having medical conditions other than low Qi.
2. Significant acute or chronic illness or other medical conditions that will prevent or interfere with giving an informed consent, or with participation in the study.
3. Persons with insulin-dependent and orally controlled diabetes will also be excluded from the study
4. Scheduling difficulties or lack of transportation that will prevent or interfere with their ability to attend all of the necessary study visits.
5. Persons medically diagnosed with depression or anxiety disorders.
6. Persons with a history of alcohol abuse or other substance abuse within the previous 2 years.
7. Females who are attempting to become pregnant, pregnant, lactating or who have given birth within 1 year.
8. Persons who have had a medical surgery in the past 4 weeks or have scheduled a surgery during the study period.
9. Persons currently enrolled in a clinical trial, or who have completed a clinical trial within the last 4 weeks.
10. Allergies to mushrooms or other fungi.
11. Significant problems with constipation or diarrhea.

12. Person exhibiting symptom of cold*(*as defined by TCM) within the past 7 days
13. A lifestyle or schedule incompatible with the study protocol.
14. Persons who are allergic to yeast products, have autoimmune disease/an immune disorder, or take antidepressants, blood thinners (anticoagulants, acetylsalicylic acid), or immunosuppressant medication

2.3 Recruitment and consent process

Subjects will be recruited through advertisement and referral from other TCM practitioners. Subjects will be documented by the referral practitioners and will not be referred without prior consent. Subjects that meet the criteria for inclusion will be enrolled. At the enrollment visit, the practitioner will independently assess the participants' PQD status: 1) via the standardized method using the PQD scoring parameters (Table 1 and 2), and 2) via conventional method using traditional TCM diagnosis of PQD status on a binary outcome (Yes/No). For each participant, the standardized and conventional assessments will be successively made at the same visit. The enrollment will start in March and concluded in April 2018.

2.4 Intervention

After the subjects are consented, a TCM practitioner will evaluate patients in a clinical setting with the objective of identifying subjects with PQD based upon the traditional, qualitative measures of TCM. Simultaneously, we will administer the Subject Record at Screening/1st visit and quantitate the participants' PQD status by employing the Standardized Diagnostic Questionnaire (Appendix I) of PQD. Subjects diagnosed as having PQD based on conventional method will be asked to return to the clinic for a second visit in which a basic physical exam (Appendix II), include that of the head, ears, eyes, nose, throat, etc., will be conducted by the PI to ensure the general health condition of subjects are compliant with the inclusion/exclusion criteria. The qualified subjects will then be re-evaluated for PQD and treated with the dietary supplement Proglucamune for 8 weeks.

Following screening, participants with PQD will begin treatment immediately. All participants will be provided with a bottle containing 60 treatment tablets in a sealed bottle and instructed to consume 2 tablets/day for the next 4 weeks. More specifically, subjects will be asked to consume 2 tablets/day of Proglucamune, a supplement currently marketed by USANA Health Sciences as a supplement that supports robust immune function. If any subjects are taking medications, they will be instructed to take the product at least 3 hours before or after the medication. Written instructions concerning how to consume the treatment, as well as information regarding treatment storage conditions and the contact information of the investigators, will be included with the dietary supplement.

Following treatment, participants will return to the clinic every 2 weeks for a period of 8 weeks for a follow-up assessment of their Protective Qi status (Figure 1). At each clinic visit, subjects will be required to undergo a TCM diagnostic work-up to assess their Protective Qi status and to complete the Subject Record at Follow-up (Appendix III). On day 28 (interim clinic visit #3), participants will return any unused treatment tablets that were provided during the first clinic visit. In addition, they will be provided with an additional allotment of 60 treatment tablets in a sealed bottle, and again instructed to consume 2 tablets/day of Proglucamune for the next 4 weeks. This will provide enough tablets for each subject to complete the study.

[figure not shown]

Figure 1 – Clinical Study Design. PQD subjects will begin a 56-day treatment on study Day 0 after initial screening. These successive interim evaluations and a final clinical assessment will be conducted every 14 days thereafter. A final clinical assessment will be performed on Day 56 and mark the end of study for subject participants.

2.5. Outcome measures

2.5.1 Primary outcome

The primary outcome will explore the proof-of-principle of β -glucan's effect on improving PQi via conventional method and via standardized method.

2.5.1.1 Change of Protective Qi Score (PQS) assessed by standardized method

Protective Qi of each participant at baseline and each follow-up visit will be measured by an on-site investigator (licensed TCM practitioners) through a standardized quantitative assessment (Table 2). The evaluation includes 3 health conditions relevant to PQD (cold frequency, symptoms, and signs). Each condition will be scored on a 1-10 scale based on a set of standardized criteria (Table 1). The sub-scores will be weighted to arrive at a final PQS. So this PQS will be on a 1-10 scale, with 10 being the most healthy state. The change of the PQS from baseline, indicating the treatment effect, will be calculated and analyzed by statistical means.

2.5.1.2 Change of Protective Qi (PQi) Status assessed by traditional method

Protective Qi status of each participant at baseline and each follow-up visit will be measured by an on-site

investigator (licensed TCM practitioners) through the qualitative traditional assessment. The status was characterized by non-PQD or PQD. The change of PQi status from baseline, indicating the treatment effect, will be calculated and analyzed by categorical statistic.

2.5.2 Secondary outcome

Since PQi is a component of Generic Qi (GQi), we will evaluate the effect of Proglucamune on the secondary outcome Generic Qi Score (GQS) and GQi status.

2.5.2.1 Change of Generic Qi Score (GQS) assessed by standardized method

Generic Qi of each participant at baseline and each follow-up visit will be measured by an on-site investigator (licensed TCM practitioners) through a standardized quantitative assessment (Table 4). The evaluation includes 5 sets of criteria indicative of Generic Qi insufficiency (cold history, symptoms of PQD, symptoms of Lung Qi Deficiency, symptoms of Heart and Spleen Deficiency, and signs of GQD). Each set will be scored on a 1-10 scales, with 10 being the most healthy state (Table 3). The sub-scores will be averaged to arrive at a final GQS. So this GQS will be on a 1-10 scale, with 10 being the most healthy state. The change of the GQS from baseline, indicating the treatment effect, will be calculated and analyzed by statistical means.

2.5.1.2 Change of Generic Qi (GQi) Status assessed by traditional method

Generic Qi status of each participant at baseline and each follow-up visit will be measured by an on-site investigator (licensed TCM practitioners) through qualitative traditional assessment. GQi status was characterized as Generic Qi Deficiency (GQD) or non-GQD. The change of GQi status from baseline, indicating the treatment effect, will be calculated and analyzed by categorical statistic.

2.6 Statistical analysis

We will follow intention-to-treat method to analyze participants' PQi and GQi change. In the case of missing data that resulted from withdrawn participants or missing visits, the PQi and GQi records from the previous visit will be used (Last Observation Carried Forward, or LOCF, imputation).

Baseline data will be imported into RStudio [15] analysis and reported using descriptive statistics.

Changes in the PQS and GQS at follow-up will be assessed using One-Way ANOVA. Change in the PQi status and GQi status will be assessed using repeated measures logistic regression.

All statistics will be conducted using RStudio.

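### Section 2.6 names a one-way ANOVA for PQS and GQS although one group is scored five times; as written it is over-conservative or does not test change from baseline

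*Combined protocol and SAP*

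**What the plan says.** Section 2.1 describes a single-arm study that "will employ a one-group pretest posttest design"; the Abstract gives 29 participants. After treatment starts, section 2.4 says "participants will return to the clinic every 2 weeks for a period of 8 weeks for a follow-up assessment", and the Figure 1 caption places the final assessment on Day 56. Each participant therefore has five scores: baseline and Days 14, 28, 42 and 56.

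Section 2.5.1 makes PQS one of two primary measures, the effect being judged "on improving PQi via conventional method and via standardized method". Section 2.5.1.1 defines the quantity of interest: "The change of the PQS from baseline, indicating the treatment effect, will be calculated and analyzed by statistical means". Section 2.5.2.1 does the same for the secondary score: "The change of the GQS from baseline, indicating the treatment effect, will be calculated and analyzed by statistical means".

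The whole specification of the test for both scores is one sentence in section 2.6: "Changes in the PQS and GQS at follow-up will be assessed using One-Way ANOVA". It gives no factor, participant term, time point or contrast with baseline. The next sentence does name a repeated-measures method, but only for the binary outcomes: "Change in the PQi status and GQi status will be assessed using repeated measures logistic regression".

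**The concern.** A one-way ANOVA compares independent groups, and this study has none: the only thing that varies is the visit, and the same people appear at every visit. The sentence can be carried out literally in two ways.

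1. **Scores by visit** (5 visits x 29 people). Stable differences between people are counted as error although they cancel from any within-person change. The F ratio is then too small.
2. **Change scores by follow-up visit** (4 visits x 29 people), the more literal reading of changes at follow-up. The null hypothesis is that mean change is the same at all four visits, not that it is zero. A gain that appears by Day 14 and holds satisfies that null exactly.

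The Abstract says the study will inform whether to go on to a randomised trial. A moderate real change in PQS could be reported as no change, and that decision would rest on it.

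**Working it through.** **Inputs from the documents.** n = 29 (Abstract); one group (2.1); five occasions (2.4, Figure 1); effect = change from baseline (2.5.1.1, 2.5.2.1). The 29 cannot be reproduced: section 2.2 refers to earlier studies and gives no effect size, SD, alpha or power.

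**Assumptions.** 5% level (two-sided for t-tests); SD 1 at every visit; within-person correlation ρ = 0.4, 0.6 or 0.8, either equal between all visits (compound symmetry, CS) or decaying with distance (AR(1)); complete data.

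**Reading 1.** F = (29 x variance of the visit means) / (average within-visit variance), on 4 and 5 x 28 = 140 df. With no change and CS, the numerator has expectation σ²(1 − ρ) and the denominator σ². F therefore centres near 1 − ρ = 0.6, 0.4, 0.2 instead of 1.

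**Reading 2.** The same ratio on four change scores, on 3 and 4 x 28 = 112 df. The shared baseline cancels between visits, so under CS the numerator has expectation σ²(1 − ρ), but the denominator is the variance of a change, 2σ²(1 − ρ). F centres near 0.5 whatever ρ is. Adding the same gain to all four visits alters neither term.

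**Comparator.** Paired t-test, Day 56 minus baseline, 28 df, noncentrality δ√29 / √(2(1 − c)), where c = ρ under CS and ρ⁴ under AR(1). For δ = 0.5 and ρ = 0.6:
- CS: 0.5 x 5.385 / √0.8 = 3.01, power 83%.
- AR(1): c = 0.1296, so 0.5 x 5.385 / √1.7408 = 2.04, power about 50%.

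**Simulation**, 20,000 trials per cell; entries are for ρ = 0.4 / 0.6 / 0.8.

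| Scenario | Structure | Reading 1 | Paired t, Day 56 |
|---|---|---|---|
| No change (type I error) | CS | 0.5 / 0.03 / 0.0% | about 5% |
| No change (type I error) | AR(1) | 2.2 / 1.0 / 0.1% | about 5% |
| Linear gain 0.3 SD | CS | 4 / 1 / 0.2% | 30 / 42 / 70% |
| Linear gain 0.3 SD | AR(1) | 10 / 7 / 3% | 20 / 22 / 30% |
| Linear gain 0.5 SD | CS | 22 / 14 / 6% | 66 / 83 / 99% |
| Linear gain 0.5 SD | AR(1) | 29 / 24 / 17% | 45 / 51 / 67% |
| Linear gain 0.75 SD | CS | 67 / 65 / 63% | 95 / 99 / 100% |
| Linear gain 0.75 SD | AR(1) | 63 / 60 / 58% | 80 / 84 / 95% |
| Linear gain 1.0 SD | CS | 96-98% | over 99% |
| Linear gain 1.0 SD | AR(1) | 89-91% | 96-99.8% |

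Linear gain by Day 56 needed for 80% power:
- CS: 0.82-0.83 SD on reading 1, against 0.59 / 0.48 / 0.34 SD paired.
- AR(1): 0.88-0.90 SD on reading 1, against 0.75 / 0.71 / 0.59 SD paired.

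On reading 2, a gain of 0.5 or 1.0 SD sustained from Day 14 is significant in 0.2-0.3% of trials under every structure, about the rate seen with no effect at all. A linear 1 SD gain is significant in 33-99.7%.

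**The case against.** **Repeated-measures ANOVA may have been meant.** Visit would be the one factor, and sections 2.1, 2.5.1.1 and 2.5.2.1 all point to within-person change. On that reading most of the power loss goes. But section 2.6 uses the term for the binary outcomes and omits it here, so an analyst following the text would fit the ordinary model. The charitable reading still lacks a baseline contrast and a sphericity correction; uncorrected, its type I error is 5.6-7.6% under AR(1) for ρ of 0.3 to 0.8.

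**The power gap mixes two things.** The paired test gains from using pairing and also from aiming at one contrast where a linear gain peaks. Against a Greenhouse-Geisser-corrected repeated-measures F, for a 0.5 SD linear gain (one-way / corrected F / paired t):
- AR(1), ρ = 0.4: 28 / 37 / 45%. Of the 45 − 28 = 17 points, 37 − 28 = 9 come from ignoring pairing.
- CS, ρ = 0.6: 14 / 72 / 82%. Of the 82 − 14 = 68 points, 72 − 14 = 58 do.

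This stands as a qualification: under AR(1) at low correlation about half the gap is due to the choice of contrast; under CS most of it is real.

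**The paired test is not always ahead.** For a 1 SD gain sustained from Day 14 under AR(1), ρ = 0.4, reading 1 has 98% power against 96%.

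**False positives are possible in one sense.** If scores rose and fell back (means 0, 0.5, 1, 0.5, 0 SD), the visit ANOVA would reject in 97-99% of trials although the Day 56 change is zero. Visits do differ there, so the rejection is correct for its own null, but it could be misread as a Day 56 benefit. That is a further reason to name the contrast.

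**Conclusion.** The concern holds. Followed literally, section 2.6 applies a test for independent groups to one repeatedly scored group, and on neither reading does it properly test the change that sections 2.5.1.1 and 2.5.2.1 define as the treatment effect. When nothing changes at any visit the error is conservative, so the cost is missed moderate effects, roughly 0.3 to 0.75 SD on reading 1 and any promptly sustained gain on reading 2.

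The percentages rest on the assumed SD, correlation, alpha and profile. The direction does not: reading 1 is conservative for any positive ρ under CS or AR(1) (at ρ = 0 it holds 5%), and positive correlation is to be expected when one practitioner scores the same people repeatedly and missing scores are carried forward. The wrong null of reading 2 does not depend on ρ at all. This should be fixed. It does not touch the separate analysis of PQi status, and a better test does not make up for the absence of a control group.

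**What to change.** Replace the sentence in section 2.6 with, for example: *The primary analysis of PQS, and the analysis of GQS, is the within-participant change from baseline to Day 56, estimated with a 95% CI by a paired t-test; other visits are supportive.* State which pre-treatment assessment is baseline, since section 2.4 has PQD assessed at screening and again before treatment. Day 56 is proposed because Figure 1 makes it the final assessment; the plan itself names no primary time point.

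A mixed model with categorical visit, unstructured within-participant covariance and small-sample degrees of freedom gives the same Day 56 contrast on complete data and may be named instead, but its handling of missing visits must then be reconciled with the LOCF rule in 2.6. A random-intercept-only model should not be used: its Day 56 contrast has 7.9 / 10.3 / 13.8% type I error under AR(1) at ρ = 0.4 / 0.6 / 0.8, while the paired t-test holds 4.8-5.2%. If repeated-measures ANOVA was meant, name it and add a sphericity correction and the Day 56 minus baseline contrast with its own paired error term.

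The cost is one sentence, with the same data and software. The paired contrast uses only two visits. For a 0.5 SD linear gain under CS it has 66 / 83 / 98.6% power against 69 / 85 / 99.0% for a random-intercept model. For a 0.5 SD gain sustained from Day 14 under AR(1) it has 46 / 50 / 67% against 48 / 56 / 80% for the corrected repeated-measures F.

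This version is dated June 2021 and enrolment was planned for March to April 2018. If the data were already in hand, say when the analysis was changed and report both results.

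### PQi status is PQD by selection at entry, so if the selecting or gating rating is the baseline, the stated logistic model gives an unusable or upward-biased change from baseline

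*Combined protocol and SAP*

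**What the plan says.** Section 2.3 defines the conventional rating as a yes/no PQD diagnosis made at the enrolment visit. Section 2.4 uses it to decide who goes forward: "Subjects diagnosed as having PQD based on conventional method will be asked to return to the clinic for a second visit". It then adds a second look: "The qualified subjects will then be re-evaluated for PQD and treated with the dietary supplement Proglucamune for 8 weeks". The next paragraph says "Following screening, participants with PQD will begin treatment immediately", and the Figure 1 legend says "PQD subjects will begin a 56-day treatment on study Day 0 after initial screening".

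The section on PQi status by the traditional method makes the same binary rating a primary outcome: "The change of PQi status from baseline, indicating the treatment effect, will be calculated and analyzed by categorical statistic". Section 2.6 names the model: "Change in the PQi status and GQi status will be assessed using repeated measures logistic regression". It gives no time coding, no correlation structure, no significance level and no provision for a constant baseline. Missing visits are filled by LOCF. Section 2.1 describes one group with no control.

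**The concern.** Subjects are chosen because a binary rating is positive, and change in that rating is then analysed. If the choosing rating is also the baseline, nobody can worsen from it, and any later reversal of the rating counts as improvement. The constant baseline also breaks one common form of the named model.

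PQi status is one of two primary measures, the other being the PQS, and the Abstract says the study will inform the decision on a randomized trial. A reader of the results could meet either an estimate that is a numerical artefact or a significant improvement produced by selection alone.

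**Working it through.** **Inputs from the documents.** 29 participants (Abstract). Baseline, then visits every 14 days to Day 56 (section 2.4, Figure 1 legend). Binary outcome. LOCF (section 2.6). No significance level, power, effect size or rate is given, so the 29 cannot be reproduced. The documents give no reversal rate, correlation, dropout or rating accuracy either; every such value below is an assumption.

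**Step 1. What the baseline can be.**
- The selecting rating is the baseline: 29/29 PQD.
- The re-rating is the baseline and also gates treatment: 29/29 PQD.
- The re-rating is the baseline and does not gate: baseline can vary. At assumed rating accuracy of 0.80 to 0.90, the chance that all 29 are again PQD is 0.001% to 3.4%.

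**Step 2. Visit as a factor, baseline as reference.** With 0/29 non-PQD at baseline, that visit contributes 29·log(1 − p0) to the log-likelihood. This is largest as p0 goes to 0, so the baseline log-odds goes to minus infinity. The contrast logit(p_visit) − logit(p0) is therefore not finite at any visit with some non-PQD ratings. This needs no assumption about rating error.

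In an illustrative data set (outcome coded as PQD), the Day 56 coefficient was −6.9 after 5 iterations, −11.9 after 10, −21.9 after 20 and −37.5 after 50. Its SE was 3.0, 37, 5,400 and 12 million. GEE on the same data was flagged as converged with SEs from 121 to 391,000, some missing. A second illustrative set (0, 3, 5, 7 and 9 of 29 non-PQD) gave a robust SE of about 1,350 under independence, and SEs in the millions or missing under an exchangeable structure. The SE depends on where the fit stops and on the working correlation, so it carries no information.

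**Step 3. Linear time, baseline kept.** Suppose the supplement does nothing and each follow-up rating is non-PQD with probability q. The expected proportions at t = 0 to 4 are 0, q, q, q, q. The least-squares slope is [(−2)(0) + (−1)q + 0·q + 1·q + 2·q]/10 = 0.2q per visit, which is upward for any q above 0. The logistic fit has a positive slope for the same reason.

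Simulation: n = 29, five visits, 20,000 trials per cell, logistic GEE with independence working correlation and robust SE. Improvement means slope z > 1.96 (assumed one-sided 2.5%); non-finite fits count as not significant.

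| Assumed reversal rate per visit | 5% | 10% | 20% | 30% |
|---|---|---|---|---|
| Baseline fixed at PQD, independent ratings | 17.8% | 31.7% | 63.9% | 85.7% |
| Baseline fixed at PQD, correlation 0.3 | 34.3% | 47.4% | 76.4% | 92.8% |
| Non-gating re-rating as baseline, independent | 4.1% | 3.1% | 2.9% | 2.9% |
| Follow-up visits only, independent | 5.2% | 3.3% | 3.0% | 3.0% |

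With correlation 0.3, the last two rows are 8.3% and 8.2% at a 5% reversal rate, and 3.1% to 4.3% at the higher rates. With LOCF and assumed dropout of 5% to 10% per visit, the first row becomes about 20% to 23%, 33% to 34%, 61% to 63% and 81% to 84%.

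**Step 4. What accuracy the reversal rates correspond to.** Take stable true status, independent rating errors, and equal sensitivity and specificity *a*. After selection on one positive rating, q = 1 − [PPV·a + (1 − PPV)(1 − a)]. With assumed prevalence 0.7 among those screened and a = 0.90, PPV = 0.63/(0.63 + 0.03) = 0.955, so q = 1 − (0.859 + 0.005) = 0.136, or 29 × 0.136 = 4.0 subjects. Over prevalence 0.5 to 0.9 and a of 0.80 to 0.95, q runs from 5.5% to 32% (1.6 to 9.3 of 29). Under this error model, in four settings with accuracy 0.80 to 0.95, the linear-time GEE rejected in 38% to 85% of 400 runs with no true change, at a two-sided 5%.

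**The case against.** The strongest answer is that the defect is conditional. Section 2.4 does plan a re-evaluation before treatment. If that is the baseline and does not gate entry, separation is unlikely at accuracy 0.80 to 0.90 and the inflation largely goes. This stands, and it is why the point is worded conditionally. However, the wording that participants with PQD start treatment, and the Figure 1 legend, favour a gated baseline, and nothing states otherwise.

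Second, the percentages rest on assumed rates. One practitioner with over 25 years of practice rates everyone (section 2.1), and nothing in the documents supports a rate as high as 20% to 30%. At accuracy 0.95 and prevalence 0.7, a single exact before-after comparison would reach significance in only 1.4% of trials. This also stands. Section 4.0 concedes that PQD lacks strict diagnostic criteria, so a reversal rate of zero cannot be presumed either. The failure in step 2 does not depend on any rate.

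Third, reversal and natural change affect any uncontrolled before-after study, and the plan is open about its design. That is so. The lack of a control is not the fault raised here; the fault is that the model adds a failure or bias of its own on top. Penalised logistic regression would give finite estimates but would not remove the selection bias.

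A reader might also infer that entry selects on GQi status in the same way. Inclusion criterion 6 ("Diagnosed as having Qi deficiency based on the following criteria") concerns Qi deficiency, and section 2.4 gates on PQD. Neither names the GQi status rating as a gate, so the documents do not establish this.

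**Conclusion.** The concern holds if the selecting rating is the baseline, or if the re-rating also gates treatment. That is the most natural reading, but not the only one. Under it, visit as a factor yields no usable change from baseline. Linear time yields false improvement in about 18% to 86% of trials across assumed reversal rates of 5% to 30% per visit, against an assumed 2.5%. The size depends on those rates, which the documents do not give, and it is nil if ratings never reverse.

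A reader might infer that the primary analysis is bound to fail, or that the separated model would produce a spuriously small p-value. The documents support neither: the baseline is undefined rather than defined wrongly, the time coding is unstated, and the fits run here returned very large or missing SEs. The PQS, the other primary measure, is outside this point. It should be fixed; confidence is medium.

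**What to change.** 1. State which conventional rating is the PQi status baseline. Reconcile the statements in section 2.4 and Figure 1 on whether a subject re-rated non-PQD before treatment is treated and analysed.
2. If baseline is PQD by selection, replace the model-based change from baseline with the proportion non-PQD at Day 56 and an exact 95% CI, reported descriptively. For example, 15/29 is 52% (33% to 71%). Give it with LOCF values as planned and again for subjects observed at Day 56, because LOCF can carry a baseline PQD forward as if observed. State that without a control it still contains rating reversal and natural change.
3. If a longitudinal model is kept, fit it to the four follow-up visits only, with the time coding stated. Describe it as trend between follow-up visits, not as a test of change from baseline or of a supplement effect.
4. If both pre-treatment conventional ratings were recorded, report the reversal rate between them as a benchmark. It will be imprecise: 3/29 would have an exact 95% CI of 2% to 27%.
5. For GQi status, report baseline GQD counts, and apply items 2 and 3 only if all or nearly all subjects are GQD.
6. Label the change post hoc if data have been seen. Version 3 is dated June 2021, and enrolment was planned for March to April 2018.

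The cost is SAP wording, with no extra visits or staff. There is no longer a p-value for change from baseline in PQi status, and a follow-up-only model misses change that is complete by Day 14.
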